## **11. ADVERSE EXPERIENCE REPORTING AND DOCUMENTATION**

### **11.1 Adverse Events**

An adverse event (AE) is any untoward medical occurrence in a clinical investigation of a patient administered a pharmaceutical product and that does not necessarily have a causal relationship with the treatment. An AE is therefore any unfavorable and unintended sign (including an abnormal laboratory finding), symptom or disease temporally associated with the administration of an investigational product, whether or not related to that investigational product. An unexpected AE is one of a type not identified in nature, severity, or frequency in the current Investigator's Brochure or of greater severity or frequency than expected based on the information in the Investigator's Brochure.

The Investigator will probe, via discussion with the subject, for the occurrence of AEs during each subject visit and record the information in the site's source documents. Adverse events will be recorded in the patient CRF. Adverse events will be described by duration (start and stop dates and times), severity, outcome, treatment and relation to study drug, or if unrelated, the cause.

## 11.2 AE Severity

The National Cancer Institute's Common Terminology Criteria for Adverse Events (CTCAE) Version 3.0 should be used to assess and grade AE severity, including laboratory abnormalities judged to be clinically significant. The modified criteria can be found in the study manual. If the experience is not covered in the modified criteria, the guidelines shown in Table 1 below should be used to grade severity. It should be pointed out that the term "severe" is a measure of intensity and that a severe AE is not necessarily serious.

**Table 1. AE Severity Grading**

Severity (Toxicity Grade)	Description
Mild (1)	Transient or mild discomfort; no limitation in activity; no medical intervention or therapy required. The subject may be aware of the sign or symptom but tolerates it reasonably well.
Moderate (2)	Mild to moderate limitation in activity, no or minimal medical intervention/therapy required.
Severe (3)	Marked limitation in activity, medical intervention/therapy required, hospitalizations possible.
Life-threatening (4)	The subject is at risk of death due to the adverse experience as it occurred. This does not refer to an experience that hypothetically might have caused death if it were more severe.

## AE Relationship to Study Drug

The relationship of an AE to the study drug should be assessed using the following the guidelines in Table 2.

**Table 2. AE Relationship to Study Drug**

Relationship to Drug	Comment
Definitely	Previously known toxicity of agent; or an event that follows a reasonable temporal sequence from administration of the drug; that follows a known or expected response pattern to the suspected drug; that is confirmed by stopping or reducing the dosage of the drug; and that is not explained by any other reasonable hypothesis.
Probably	An event that follows a reasonable temporal sequence from administration of the drug; that follows a known or expected response pattern to the suspected drug; that is confirmed by stopping or reducing the dosage of the drug; and that is unlikely to be explained by the known characteristics of the subject's clinical state or by other interventions.

Possibly	An event that follows a reasonable temporal sequence from administration of the drug; that follows a known or expected response pattern to that suspected drug; but that could readily have been produced by a number of other factors.
Unrelated	An event that can be determined with certainty to have no relationship to the study drug.

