### 2.2 Risk / Benefit Assessment

**Lorcaserin is an FDA-approved medication that is well-tolerated with relatively few adverse events (AEs).** Three Phase 3 trials (cumulative N=7789) that evaluated lorcaserin's treatment effect on obesity have established its safety among patients with and without diabetes. The most

common reported side effects for lorcaserin include headaches, dizziness, fatigue, nausea, dry mouth, and constipation. In these trials, 8.6% of individuals given lorcaserin discontinued treatment as a result of AEs, compared to 6.7% individuals given placebo. Aside from pregnancy, there are no contraindications for lorcaserin. Nevertheless, the safety and tolerability of lorcaserin among active cocaine users is unknown. **Lorcaserin has a low potential for abuse.** The frequency of AEs associated with lorcaserin increases when taken above the therapeutic dose, which may limit abuse potential. A double-blind randomized crossover study to test abuse liability found that lorcaserin was similar to placebo with respect to subjective liking, overall liking, and ratings on desire to take the drug again. Exceeding the recommended lorcaserin dose levels (10 mg, twice daily) were associated with higher levels of known unpleasant side effects and subjective dislike, compared to placebo. Thus, lorcaserin dose escalation would result in primarily negative subjective effects; these self-regulating properties will likely limit the medication's abuse liability.

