### 15.3 Analysis of Primary Endpoint

To establish the feasibility of enrolling and retaining 45 MSM with cocaine use disorder in a 12 week with 2:1 randomized, double-blind study of lorcaserin versus placebo. We will calculate the following feasibility measures: 1) proportion of those eligible among those screened; 2) proportion enrolled among those eligible; and 3) study completion rate. Process measures (e.g., visit length, counseling session completion) and reactions to study procedures will also be collected and reported. Between-group differences will be assessed using Fisher's exact and Wilcoxon rank sum tests. We will also calculate Kaplan-Meier curves for time to dropout, by group, and test for differences using the log-rank test. Precision: In the overall sample of 45, proportions will be estimated with margins of sampling error (MSEs; i.e., half widths of 95% confidence intervals) of  $\leq 14.4$  percentage points, and means with MSEs of 0.30 standard deviations, both typical for a small pilot study. While the study will only be powered to detect large between-group differences in process measures, it will provide warning of potential problems.

To explore the tolerability of lorcaserin versus placebo among MSM with cocaine use disorders, as determined by the number of adverse clinical events in the cocaine and placebo arms. We will compute the proportions of those experiencing adverse events, both overall and by type. Adverse clinical events, AEs and SAEs, and other binary safety outcomes will be presented as percent of participants that experience the safety outcome by treatment assignment. We will also classify AEs as any AE that results in stopping study medication, specific common AEs ( $>2\%$  in both groups), AEs for general organ system categories, and AEs potentially related to study drug. The probability of observing at least one AE with population incidence of 1, 2, and 5% in the active arm will be 26, 45, and 70% with 2:1 randomization, respectively.

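### The causality table has no class for a new event of uncertain cause and lets any known side effect be graded definitely related, so the related-AE tables can mislead

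*Combined protocol and SAP*

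**What the plan says.** Under the heading AE Relationship to Study Drug, which follows section 11.2, the protocol states: "The relationship of an AE to the study drug should be assessed using the following the guidelines in Table 2". This is the four-row causality table in section 11, not the procedures table in Appendix 1 that carries the same number. Its rows are:

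- *Definitely*: "Previously known toxicity of agent; or an event that follows a reasonable temporal sequence from administration of the drug". The second alternative goes on to require a recognised response pattern, confirmation when the drug is stopped or reduced, and no other reasonable explanation.
- *Probably*: the same timing, pattern and confirmation conditions, with other explanations unlikely.
- *Possibly*: reasonable timing, and an event "that follows a known or expected response pattern to that suspected drug; but that could readily have been produced by a number of other factors", with no need for confirmation on stopping or reducing the drug.
- The fourth row, *Unrelated*, asks for certainty: "An event that can be determined with certainty to have no relationship to the study drug".

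No row covers unlikely, unknown or unassessable events.

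Relationship to drug is recorded on the CRF for each AE (sections 9.1 and 11.1). It is then used twice. Section 15.3 lists "AEs potentially related to study drug" as one of four additional AE classifications, and section 15.4 tabulates relationship by treatment group. Neither section says which rows of Table 2 count as potentially related.

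**The concern.** A causality scale should give every event one class. This one appears to fail in two ways.

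First, section 11.1 defines unexpected AEs, and section 2.2 says that "the safety and tolerability of lorcaserin among active cocaine users is unknown". A toxicity particular to this population would probably not match a recognised pattern, yet three rows need such a pattern or a known toxicity and the fourth needs certainty of no relationship. The assessor must still enter something on the CRF. Two assessors may choose differently, and a new signal may be entered as *Unrelated*.

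Second, section 2.2 says that the most "common reported side effects for lorcaserin include headaches, dizziness, fatigue, nausea, dry mouth, and constipation". These are non-specific symptoms. If being a known toxicity is enough for *Definitely*, the top class will hold events that merely resemble the drug's profile. Grading is blind (section 8.2), so this happens on placebo too.

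At stake is whether the two relatedness displays can be relied on when tolerability, part of the primary objective in section 3.1, is summarised for a larger trial.

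**Working it through.** The plan gives no figure to reproduce here, so the check is logical: list every combination of the criteria that Table 2 itself uses and see which rows each one meets.

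**Inputs, all from Table 2**

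- Timing plausible: yes or no (2 levels).
- Event type: no recognised pattern; recognised pattern but not a listed toxicity; known toxicity, taken as always fitting a recognised pattern (3 levels).
- Confirmed on stopping or reducing the drug: yes or no (2 levels).
- Other cause: none, unlikely, readily available, or certain (4 levels).

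Combinations: 2 × 3 × 2 × 4 = 48.

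**Rules as written**

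- *Definitely*: known toxicity, or (timing and pattern and confirmation and no other cause).
- *Probably*: timing and pattern and confirmation, with other cause none or unlikely.
- *Possibly*: timing and pattern, with other cause readily available.
- *Unrelated*: other cause certain.

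**Combinations that meet no row**

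- No recognised pattern and no certain other cause: 2 timing × 2 confirmation × 3 cause = 12. Six of these have plausible timing.
- Recognised pattern but not a listed toxicity, implausible timing, no certain other cause: 2 × 3 = 6.
- Recognised pattern but not a listed toxicity, plausible timing, no confirmation, other cause none or unlikely: 2.
- Total: 12 + 6 + 2 = 20 of 48.

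**Known toxicities**

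All 2 × 2 × 4 = 16 combinations meet *Definitely*. Four of them, those with a certain other cause, also meet *Unrelated*.

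**Combinations that meet more than one row**

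| Rows met | Combinations |
|---|---|
| *Definitely* and *Unrelated* | 4 |
| *Definitely* and *Probably* | 3 |
| *Definitely* and *Possibly* | 2 |
| Total | 9 |

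**The same enumeration under candidate edits**

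| Edit | No class | More than one class |
|---|---|---|
| As written | 20 | 9 |
| Drop the pattern requirement from *Possibly* only | 18 | 9 |
| Change the 'or' to 'and' in *Definitely*, and drop the pattern requirement from *Possibly* | 26 | 1 |
| Delete the known-toxicity clause only | 28 | 2 |
| Delete the clause, widen *Possibly*, add *Unlikely* | 0 | 2 |
| The same, with *Probably* limited to events that do not meet *Definitely* | 0 | 0 |

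In the last row the 48 combinations divide as *Definitely* 2, *Probably* 2, *Possibly* 14, *Unlikely* 18 and *Unrelated* 12, which sum to 48.

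**The case against.** The strongest reply is that little of the tolerability analysis depends on this table. Section 15.3 reports the proportions with AEs overall and by type, by arm, and none of that uses relatedness. A new toxicity would still appear there and in the organ-system grouping, and section 17.2 sends SAEs to the IRB regardless of causality. This stands. A reader might infer that the tolerability result itself is wrong; the documents do not support that.

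A reader might also infer that a new event cannot be counted as related at all. That goes too far. Table 2 is offered as guidelines, so an assessor may put such an event under *Possibly*. Because the plan does not define potentially related, the count could also be taken as everything not graded *Unrelated*. What stands is that the outcome is left to the assessor and the analyst.

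Third, the known-toxicity clause has little effect on a collapsed related count. A well-timed headache with ready alternative causes already meets *Possibly*, so the clause mostly moves events between related grades. Blind grading applies it to both arms, so it need not favour either. This also stands. One might try to size the effect by applying a background symptom rate to the placebo arm. The documents give no such rate, and the product would count people with symptoms rather than events whose class changes.

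Finally, the punctuation could be read so that the later conditions also bind known toxicities. That reading is strained, and the 12 unclassed combinations without a recognised pattern remain under it.

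**Conclusion.** The point holds as a minor but real wording defect. The missing class for an unexpected, plausibly timed event of uncertain cause is the more important half: it does not depend on how the known-toxicity clause is read, and it can remove events from the related count. The clause is secondary; it can inflate the *Definitely* column in both arms and makes classes overlap.

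The consequence is confined to the related-AE grouping in section 15.3 and the relationship table in section 15.4, which can be misstated if Table 2 is applied literally. The all-cause AE proportions are not affected, and no bias between arms is shown.

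The size can be stated only as logic: 20 of 48 combinations unclassed and 9 classed more than once. The combinations are not equally likely, so these are not event rates. They rest on a plain reading of the clause and on treating every known toxicity as fitting a recognised pattern.

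**What to change.** Make these changes to Table 2 together; deleting the clause alone would raise the unclassed combinations from 20 to 28.

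1. *Definitely*: delete the opening known-toxicity alternative and keep the remaining conditions. Do not change the 'or' to 'and'. That would restrict the class to toxicities already known, and it leaves 26 combinations unclassed even with the pattern requirement dropped from *Possibly*.
2. *Possibly*: cover any event with a reasonable temporal sequence that does not meet *Definitely* or *Probably* and is not certainly unrelated, with no pattern or other-cause condition.
3. Add *Unlikely* as a residual class for events without plausible timing that are not certainly unrelated.
4. State that an event takes the highest related class it meets, so that one meeting *Definitely* is not also *Probably*.
5. In section 15.3 or the SAP, state which classes count as potentially related.

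The cost is one table, one CRF code list and one sentence in the analysis section, ideally before any AE is graded. The downside is that somewhat more events will be graded *Possibly*.

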### 11.3 Serious Adverse Experiences (SAE)

An SAE is defined as any AE occurring at any dose that results in any of the following outcomes:

- death
- a life-threatening adverse experience
- inpatient hospitalization or prolongation of existing hospitalization
- a persistent or significant disability/incapacity
- a congenital anomaly/birth defect

Other important medical events may also be considered an SAE when, based on appropriate medical judgment, they jeopardize the subject or require intervention to prevent one of the outcomes listed.

## 12. DISCONTINUATION AND REPLACEMENT OF SUBJECTS

### 12.1 Early Discontinuation of Study Drug

A subject may be discontinued from study treatment at any time if the subject or the investigator feels that it is not in the subject's best interest to continue. The following is a list of possible reasons for study treatment discontinuation:

- Subject withdrawal of consent (or assent)
- Subject is not compliant with study procedures
- Adverse event that in the opinion of the investigator would be in the best interest of the subject to discontinue study treatment

- Protocol violation requiring discontinuation of study treatment
- Lost to follow-up
- PI or clinician request for early termination of study
- Positive pregnancy test (females)

If a subject is withdrawn from treatment due to an adverse event, the subject will be followed and treated by the Investigator until the abnormal parameter or symptom has resolved or stabilized.

All subjects who discontinue study treatment should come in for an early discontinuation visit as soon as possible and then should be encouraged to complete all remaining scheduled visits and procedures.

All subjects are free to withdraw from participation at any time, for any reason, specified or unspecified, and without prejudice.

Reasonable attempts will be made by the investigator to provide a reason for subject withdrawals. The reason for the subject's withdrawal from the study will be specified in the subject's source documents. Refer to Section 10 for early termination procedures.

## **12.2 Withdrawal of Subjects from the Study**

A subject may be withdrawn from the study at any time if the subject or the investigator feels that it is not in the subject's best interest to continue.

All subjects are free to withdraw from participation at any time, for any reason, specified or unspecified, and without prejudice.

Reasonable attempts will be made by the investigator to provide a reason for subject withdrawals. The reason for the subject's withdrawal from the study will be specified in the subject's source documents. As noted above, subjects who discontinue study treatment early (i.e., they withdraw prior to Week 8 Visit ) should have an early discontinuation visit. Refer to Section 10 for early termination procedures. Subjects who withdraw after Week 8 Visit but prior to Week 12 Visit should be encouraged to come in for a final visit (and the procedures to be followed would include those for their next scheduled visit).

## **12.3 Replacement of Subjects**

Subjects who withdraw from the study treatment will not be replaced.

## **13. PROTOCOL VIOLATIONS**

A protocol violation occurs when the subject or investigator fails to adhere to significant protocol requirements affecting the inclusion, exclusion, subject safety and primary endpoint criteria. Protocol violations for this study include, but are not limited to, the following:

[figure not shown]
- Failure to meet inclusion/exclusion criteria
- Use of a prohibited concomitant medication (such as those listed in the exclusion criteria)

Failure to comply with Good Clinical Practice (GCP) guidelines will also result in a protocol violation. The PI will determine if a protocol violation will result in withdrawal of a subject.

When a protocol violation occurs, it will be discussed with the investigator and a Protocol Violation Form detailing the violation will be generated. This form will be signed by a Sponsor representative and the Investigator. A copy of the form will be filed in the site's regulatory binder and in the Sponsor's files.

## 14. DATA SAFETY MONITORING

The PI along with the site physician [name], will be responsible for ensuring proper monitoring of the safety and efficacy of this trial, including the execution of the DSM plan, and complying with the reporting requirements, including reports to the IRB, DSMB, NIDA and (where applicable) the FDA (see Figure 1 below).

or, meets weekly to discuss all aspects of the study such as recruitment and retention, clinical or counseling issues, and any regulatory or operation issues. All study documents are monitored by the study coordinator for quality assurance on a weekly basis to ensure timely corrections to charting such as missing initials or cross-outs with error-correction. Although there is no outside monitor, the clinicians review each other's charts for accuracy, consistency, and adherence to protocol. Regular audits will be conducted as well on consent forms, laboratory logs and other data collection forms.

The interim DSMB report will contain a brief description of the trial, baseline socio-demographic characteristics of participants, retention and disposition of study participants, a description of any quality assurance or regulatory issues, a report of AEs and SAES, and the status of outcome data.

**Members and affiliation:** We will use the existing University of California, Los Angeles (UCLA) Data & Safety Monitoring Board for Addiction Medicine (DSMBAM), which has extensive experience in monitoring pharmacologic interventions, including among vulnerable populations. The DSMBAM has monitored all of our pharmacologic trials for substance users.

To ensure that the DSMB oversight of the study remains independent from the proposed study, the PI([name]) as well as others who serve on the DSMBAM that might be linked with the study in some way recuse themselves from review of the present study.

The purpose of the DSMBAM is to provide oversight and monitoring of Phase I and Phase II clinical trials of pharmacological and behavioral treatments for stimulant dependence. There are three fundamental charges of the board, which are:

- To ensure the safety of trial participants
- To preserve validity and integrity of research data
- To facilitate the availability of timely as well as reliable findings to the broader clinical community

Below are members who serve as committee chairs as well as clinical research experts:

participants, reasons to discontinue treatment, outcome measures, sample size target, key adherence and safety variables, and the data analysis plan.

Subsequent ongoing reviews include: enrollment data, including those screened, enrolled, and active; subject eligibility; demographic characteristics of participants (total, and by group), recruitment and retention (total and by group). Protocol compliance are evaluated by reviewing: the expected recruitment rate, study drop-outs and reasons for leaving the study, data quality assurance reports, overall data flow procedures, CRFs collected, received, and entered; protocol deviations; protocol violations; missing data; staff omissions; subject refusal to provide data; adherence to stopping rules. The data safety report are provided in total and by group, and include any relevant medical, psychosocial or laboratory data, AEs summarized in tables, individual SAE reports, concomitant medications, and concomitant illnesses. The outcome data report includes outcome data analyzed by group, masked or unblended, with or without statistical analyses, and include all outcome variables.

